8.3.3.2. Assessment of adverse events**8.3.3.2.1. Assessment of intensity**

The intensity of the following solicited AEs will be assessed as described in [Table 13](#).

Table 13 Intensity scales for solicited symptoms in adults

Adverse Event	Intensity grade	Parameter
Pain at injection site	0	None
	1	Mild: Any pain neither interfering with nor preventing normal every day activities.
	2	Moderate: Painful when limb is moved and interferes with every day activities.
	3	Severe: Significant pain at rest. Prevents normal every day activities.
Redness at injection site		Record greatest surface diameter in mm
Swelling at injection site		Record greatest surface diameter in mm
Fever*		Record temperature in °C/F
Headache	0	Normal
	1	Mild: Headache that is easily tolerated
	2	Moderate: Headache that interferes with normal activity
	3	Severe: Headache that prevents normal activity
Fatigue	0	Normal
	1	Mild: Fatigue that is easily tolerated
	2	Moderate: Fatigue that interferes with normal activity
	3	Severe: Fatigue that prevents normal activity
Gastrointestinal symptoms (nausea, vomiting, diarrhoea and/or abdominal pain)	0	Normal
	1	Mild: Gastrointestinal symptoms that are easily tolerated
	2	Moderate: Gastrointestinal symptoms that interfere with normal activity
	3	Severe: Gastrointestinal symptoms that prevent normal activity
Myalgia	0	Normal
	1	Mild: Myalgia that is easily tolerated
	2	Moderate: Myalgia that interferes with normal activity
	3	Severe: Myalgia that prevents normal activity
Shivering	0	None
	1	Shivering that is easily tolerated
	2	Shivering that interferes with normal activity
	3	Shivering that prevents normal activity

* The preferred route for recording temperature in this study is oral. When there is no other alternative, the temperature may be recorded by other route. If the temperature is taken by another route (axillary, rectal or tympanic), the route should be documented.

Note: Temperature will be recorded in the evening. Should additional temperature measurements be performed at other times of day, the highest temperature will be recorded in the eCRF and the time when the temperature was recorded.

The maximum intensity of local injection site redness/swelling will be scored at GSK Biologicals as follows using GSK Biologicals' standard grading scale based on the US Food and Drug Administration (FDA) guidelines for Toxicity Grading Scale for Healthy Adult and Adolescent Volunteers enrolled in Preventive Vaccine Clinical Trials [FDA, 2007]:

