10.7. Interpretation of analyses

There is no pre-defined success criterion for the primary objective assessment. The analyses remain descriptive.

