**Table 1 Details of subgroups**

Sub-group category	Sub-group order in tables	Sub-group label in tables	Sub-group definition for footnote
Age	1	50-59 YOA	50-59 year old subjects
	2	60-69 YOA	60-69 year old subjects
	3	≥ 70 YOA	≥ 70 year old subjects
Frailty Index (FI)	1	Non-Frail	Subjects with frailty index <=3 are considered as Non frail
	2	Pre-Frail	Subjects with frailty index >3 and <=8 are considered as pre fail
	3	Frail	Subjects with frailty index >8 are considered as frail
Maximum Intensity / Reactogenicity Grade	1	Grade 0	Subjects with no solicited symptoms reported.
	2	Grade 1,2	Subjects with at least one grade 1 or 2 (=mild or moderate) solicited AE reported as maximum intensity.
	3	Grade 3	Subjects with at least one grade 3 (=Severe) solicited AE reported as maximum intensity.
Type of Symptom*	1	None	Subjects with no solicited symptom reported
	2	Local	Subjects with at least one solicited local symptom reported
	3	General	Subjects with at least one solicited general symptom reported
Gender	1	Male	Male Subjects
	2	Female	Female Subjects

\*Note that a subject can be included in both Local or General categories

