#### **3.2. Secondary objectives**

- To estimate the change in the SF-36 PF scale score from baseline score to the mean score over the period day 1 to day 7 following the second HZ/su vaccination in subjects  $\geq 50$  YOA overall.
- To estimate the change in the SF-36 PF scale score in subjects  $\geq 50$  YOA by age, gender and reactogenicity grade and type of symptom (local, systemic) from baseline score to the mean score over the period day 1 to day 7 following both HZ/su vaccinations 1 and 2.
- To estimate the change in SF-36 PF single item scores in subjects  $\geq 50$  YOA overall, by age, gender and reactogenicity grade and type of symptom (local, systemic) from baseline score to the mean score over the period day 1 to day 7 following both HZ/su vaccinations 1 and 2.
- To estimate the change in SF-36 Role Physical scores in subjects  $\geq 50$  YOA overall, by age, gender and reactogenicity grade and type of symptom (local, systemic) from baseline score to the score on day 7 following both HZ/su vaccinations 1 and 2.
- To estimate the QALY change in subjects  $\geq 50$  YOA overall, by age, gender, reactogenicity grade and type of symptom (local, systemic) from baseline score to the combined score on days 1 to 7 following both HZ/su vaccinations 1 and 2.
- To assess the impact of reactogenicity on the healthcare resource utilization (i.e., hospitalization, General Practitioners and specialist visits, medication intake) in subjects  $\geq 50$  YOA overall, by age, gender reactogenicity grade and type of symptom (local, systemic) following both HZ/su vaccinations 1 and 2.
- To estimate the work loss in subjects  $\geq 50$  YOA overall, by age, gender, reactogenicity grade and type of symptom (local, systemic) following both HZ/su vaccinations 1 and 2.
- To estimate the work loss for non-dedicated caregivers (e.g., family member) of subjects  $\geq 50$  YOA overall, by gender, reactogenicity grade and type of symptom (local, systemic) following both HZ/su vaccinations 1 and 2.

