### 6.2.1. SF-36 and EQ-5D

The SF-36 health survey and the EQ-5D questionnaires will be completed by all subjects at each study visits (i.e., Visit 1 Day -7, Visit 2 Month 0 (before the vaccination), Visit 3 Day 7, Visit 4 Month 2 (before the vaccination) and Visit 5 Day 67). Additionally, after each vaccination, the subjects will be given the questionnaires to take home and asked to complete only questions 3a through 3j of the SF-36 questionnaires and the entire EQ-5D questionnaires, on a daily basis on Days 1 to 6 post-vaccination.

Each of the 8 components of the SF-36 Questionnaire and the EQ-5D Utility and VAS scores will be presented at each scheduled visit (Day -7, Day 0, Day 7, Day 60 and Day 67) including the derived baseline values for each dose. In addition the SF-36 physical functioning score (PF) (based on questions 3a to 3j) and the EQ-5D utility and VAS scores will be presented on days 1 to 6 following each dose. Further details of the SF-36 components and EQ-5D Utility and VAS scores can be found in section [7.1.3](#).

The primary endpoint variable is the SF-36 Physical Functioning (PF) scale. The analysis will be performed on the subgroups detailed in [Table 1](#).

The 10 individual questions that form the SF-36 PF scale will be analysed on an individual basis. The three responses (Limited a lot, Limited a little, Not limited at all) to the individual questions will be assigned a score of 0, 50, or 100. In this way a baseline score and a mean score over the 7 days post each dose can be calculated for each individual question. Summary statistics of the change from baseline will be presented for each individual question.

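### The Local and General rows in SAP Table 1 may share subjects, so the secondary results by symptom type cannot show the impact of local reactions alone; exclusive rows would be a cheap improvement.

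*SAP*

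**What the plan says.** SAP 3.2, like Protocol 2.2, states the PF objective "by age, gender and reactogenicity grade and type of symptom (local, systemic"). The PF single-item, Role Physical and QALY objectives carry the same breakdown.

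SAP Table 1 (section 2) defines the rows:

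- **Type of symptom:** None, Local, General. Local requires at least one solicited local symptom and General at least one solicited general symptom. The footnote reads: "Note that a subject can be included in both Local or General categories". There is no row for local symptoms only, general symptoms only, or both.
- **Grade:** Grade 0 ("Subjects with no solicited symptoms reported"), one pooled row for Grades 1 and 2 ("Subjects with at least one grade 1 or 2 (=mild or moderate) solicited AE reported as maximum intensity"), and Grade 3.

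SAP 6.2.1, in the paragraph on the PF scale, says: "The analysis will be performed on the subgroups detailed in" Table 1. No other part of the visible SAP defines symptom type differently or splits Grades 1 and 2 for the quality-of-life outcomes.

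Protocol Table 13 separates the two pooled grades by effect on activity for several symptoms. For fatigue, Grade 1 is "Mild: Fatigue that is easily tolerated" and Grade 2 is "Moderate: Fatigue that interferes with normal activity". Protocol 10.7 says of the whole plan: "The analyses remain descriptive".

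**The concern.** A reader given a Local row and a General row will compare them as local against systemic impact. They are not separate groups. A subject with a sore arm and two days of myalgia counts in both, and any loss of function from the myalgia then appears in the Local row too. With no hypothesis test planned, the displayed categories are the whole answer to these objectives. The study is meant to help vaccinators tell people what to expect (Protocol 1.2.1), and the effect of a local reaction alone is a natural question that the rows cannot answer.

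A smaller matter is the pooled grade row. For pain, headache, fatigue, gastrointestinal symptoms, myalgia and shivering, the step from tolerated or non-interfering to interfering lies between Grades 1 and 2. The pooled row cannot show whether function changes at that step.

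**Working it through.** **Inputs.** SD of PF change 21.2, 360 evaluable subjects, precision 2.2, 400 enrolled (Protocol 10.3). Injection-site pain up to 70% of people, myalgia and fatigue about 33% overall/dose, grade 3 local pain about 4% (Protocol 1.2.1). The documents give no rate for any local symptom, any general symptom, Grade 1 or Grade 2. I use L = 0.70 for local, and G = 0.33 or an assumed 0.50 for general. One source rate is per person and the other per dose, so everything after step 1 is illustration.

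**1. The plan's own figure.** Half-width = 1.96 × SD/√n = 1.96 × 21.2/√360 = 2.19, against 2.2 stated. The confidence level is not given there; 95% two-sided reproduces it. 360/(1 − 0.10) = 400.

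**2. How much of the Local row is also General.** The overlap lies between max(0, L + G − 1) and min(L, G), and is L × G under independence. Dividing by L gives the share of the Local row:

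| G | Minimum | Independence | Maximum |
|---|---|---|---|
| 0.33 | 0.03/0.70 = 4% | 0.231/0.70 = 33% | 0.33/0.70 = 47% |
| 0.50 | 0.20/0.70 = 29% | 0.35/0.70 = 50% | 0.50/0.70 = 71% |

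At the maximum, every General subject is also a Local subject.

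**3. Size and precision of exclusive rows** (independence, SD 21.2 in each cell, half-width 1.96 × 21.2/√n):

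| Row | Formula × 360 | G = 0.33 | G = 0.50 |
|---|---|---|---|
| Local only | L(1 − G) | 169 (3.2) | 126 (3.7) |
| Both | LG | 83 (4.6) | 126 (3.7) |
| General only | (1 − L)G | 36 (6.9) | 54 (5.7) |
| None (existing row) | (1 − L)(1 − G) | 72 (4.9) | 54 (5.7) |

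General only ranges from 0, if general symptoms occur only with local ones, to 0.30 × 360 = 108 at minimum overlap (half-width 4.0).

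**4. Grade rows.** None runs from 0% (minimum overlap) to 30% (General nested in Local). With Grade 3 at 4% to an assumed 10%, the pooled row holds 360 × (1 − 0.30 − 0.10) = 216 to 360 × (1 − 0 − 0.04) = 346 subjects. If an assumed 20% to 50% of these are Grade 2, that row holds 0.20 × 216 = 43 to 0.50 × 346 = 173 (half-width 6.3 to 3.2). These counts use all solicited symptoms; a restricted version may differ.

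To show what pooling can do, with invented values: a change of 0 in Grade 1 and −10 in Grade 2, with 30% at Grade 2, displays as 0.70 × 0 + 0.30 × (−10) = −3.0.

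**5. Are the data there?** Yes. SAP Figures 2 and 4 show separate eCRF questions for general and local symptoms, with daily intensity or size from Day 0 to Day 6.

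**The case against.** The objectives do not ask for exclusive types or for separate Grades 1 and 2. The overlap is footnoted, the analyses are descriptive, and Grade 3, the grade whose meaning for function the rationale calls unclear, has its own row. All of that stands. A reader might infer that Table 1 contradicts the objectives; it does not, because it is a literal, coarse answer. The layout of the QoL tables is in TFL2, which is not among the documents, so finer rows there cannot be ruled out.

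Exclusive rows would not fully isolate type. Subjects with both kinds of symptom may also have stronger reactions, so Local only against Both partly reflects severity. General only may be very small. These limits stand, but the current Local row is open to the same severity mixing and also hides the overlap.

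On grades, it is tempting to say that splitting the pooled row as it stands would reveal the step to interference. It would not do so cleanly. The maximum grade also covers redness and swelling in mm and fever in °C (SAP 7.1.2.1). A subject with 60 mm redness and otherwise only tolerated symptoms is Grade 2 with nothing that interferes. A split is useful only over the symptoms graded by effect on activity, and it remains optional.

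**Conclusion.** The point holds as a cheap improvement to the secondary analyses. Followed as written, the visible SAP gives no estimate for subjects with local symptoms alone, although the objectives are stated by type. None is already exclusive; the missing rows are Local only, General only and Both.

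Two stronger conclusions are not supported. A reader might infer that the overlap biases the PF results. The difference in PF change between subjects with both types and those with local symptoms only is not in the documents, so no bias in PF points can be shown. Nor is the primary objective touched, since it is estimated in all subjects after the first dose.

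The figures rest on single-symptom rates standing in for any local or any general symptom, on independence, and on one SD for every cell. On that basis a third to a half of the Local row would also have general symptoms (4% to 71% over the full bounds). Local only and Both would have usable precision; General only might not.

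**What to change.** - **Main change.** Keep every current row of Table 1. For PF, PF single items, Role Physical and QALY, after each dose, add Local only, General only and Both, each with N and 95% CI. Restrict these rows to subjects whose local and general questions were both answered Yes or No. SAP 7.2.2.4 accepts either one for the combined analysis, and an unanswered question must not be read as absence. The existing None row is the reference and is not duplicated.
- **Optional.** Beside the pooled Grade 1,2 row, show Grade 1 and Grade 2 separately, using the maximum grade over pain, headache, fatigue, gastrointestinal symptoms, myalgia and shivering.
- **Editorial.** State which grade row holds a subject whose only reaction is redness or swelling under 20 mm (graded 0 in SAP 7.1.2.1 but a documented symptom under 7.2.2.3), or whose only symptom is a Yes with no daily value. The number affected is unknown.

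If TFL2 already contains these rows, it is enough to align Table 1 with it.

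**Cost.** No new data, and no row lost or redefined. The output grows: PF, ten items, Role Physical and QALY make 13 outcomes, so three rows over two doses add 13 × 3 × 2 = 78 estimates, and the optional grade rows add 13 × 2 × 2 = 52. Some cells will be imprecise, General only above all, and a note should say that Local only against Both may also reflect severity.

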### **3. OBJECTIVES**

#### **3.1. Primary objective**

To estimate the change in the SF-36 Physical Functioning (SF-36 PF) scale score from baseline score to the mean score over the period day 1 to day 7 following the first HZ/su vaccination in subjects  $\geq 50$  years of age (YOA) overall.

#### **3.2. Secondary objectives**

- To estimate the change in the SF-36 PF scale score from baseline score to the mean score over the period day 1 to day 7 following the second HZ/su vaccination in subjects  $\geq 50$  YOA overall.
- To estimate the change in the SF-36 PF scale score in subjects  $\geq 50$  YOA by age, gender and reactogenicity grade and type of symptom (local, systemic) from baseline score to the mean score over the period day 1 to day 7 following both HZ/su vaccinations 1 and 2.
- To estimate the change in SF-36 PF single item scores in subjects  $\geq 50$  YOA overall, by age, gender and reactogenicity grade and type of symptom (local, systemic) from baseline score to the mean score over the period day 1 to day 7 following both HZ/su vaccinations 1 and 2.
- To estimate the change in SF-36 Role Physical scores in subjects  $\geq 50$  YOA overall, by age, gender and reactogenicity grade and type of symptom (local, systemic) from baseline score to the score on day 7 following both HZ/su vaccinations 1 and 2.
- To estimate the QALY change in subjects  $\geq 50$  YOA overall, by age, gender, reactogenicity grade and type of symptom (local, systemic) from baseline score to the combined score on days 1 to 7 following both HZ/su vaccinations 1 and 2.
- To assess the impact of reactogenicity on the healthcare resource utilization (i.e., hospitalization, General Practitioners and specialist visits, medication intake) in subjects  $\geq 50$  YOA overall, by age, gender reactogenicity grade and type of symptom (local, systemic) following both HZ/su vaccinations 1 and 2.
- To estimate the work loss in subjects  $\geq 50$  YOA overall, by age, gender, reactogenicity grade and type of symptom (local, systemic) following both HZ/su vaccinations 1 and 2.
- To estimate the work loss for non-dedicated caregivers (e.g., family member) of subjects  $\geq 50$  YOA overall, by gender, reactogenicity grade and type of symptom (local, systemic) following both HZ/su vaccinations 1 and 2.

# Statistical Analysis Plan

Study alias & e-track number(s): ZOSTER-063 (204928)

- To estimate the extra work for dedicated caregivers of subjects  $\geq 50$  YOA overall, by gender, reactogenicity grade and type of symptom (local, systemic) following both HZ/su vaccinations 1 and 2.
- To evaluate the safety and reactogenicity following administration of the HZ/su vaccine in subjects  $\geq 50$  YOA.

## 4. ENDPOINTS

### 4.1. Primary endpoints

- Change in mean SF-36 PF scale score.
  - Baseline\* versus mean score over the period day 1 to day 7\*\* after first vaccination.

### 4.2. Secondary endpoints

- Change in mean SF-36 PF scale score.
  - Baseline\* versus mean score over the period day 1 to day 7\*\* after second vaccination.
- Change in mean SF-36 PF single item scores.
  - Baseline\* versus mean score over the period day 1 to day 7\*\* after each vaccination.
- Change in SF-36 Role Physical scores.
  - Baseline\* versus score on day 7\*\* after each vaccination.
- Change in the QALY.
  - Baseline\* versus combined score over the period day 1 to day 7\*\* after each vaccination.
- Healthcare resource utilization (i.e., hospitalization, telephone calls, medical visits and specialist visits, medication intake).
  - Days 0 to 6 after each vaccination.
- Work loss for subjects.
  - Days 0 to 6 after each vaccination.
- Work loss for the non-dedicated caregivers.
  - Days 0 to 6 after each vaccination.
- Extra work for dedicated caregivers.

# Statistical Analysis Plan

Study alias & e-track number(s): ZOSTER-063 (204928)

- Days 0 to 6 after each vaccination.
- Solicited local and general symptoms in subjects.
  - Occurrence, intensity and duration of solicited local symptoms within 7 days (Days 0-6\*\*) after each vaccination.
  - Occurrence, intensity, duration and relationship to vaccination of solicited general symptoms within 7 days (Days 0-6\*\*) after each vaccination.
- Unsolicited adverse events (AEs) in subjects.
  - Occurrence, intensity and relationship to vaccination during 30 days (Days 0-29) after each vaccination, according to the Medical Dictionary for Regulatory Activities (MedDRA) classification.
- Occurrence of serious adverse events (SAEs).
  - Occurrence and relationship to vaccination of all SAEs from the first vaccination up to the study end.
- Occurrence of adverse events of specific interest (AESIs): potential Immune-Mediated Diseases (pIMDs).
  - Occurrence and relationship to vaccination of any pIMDs from first vaccination up to the study end.

\*Note: baseline for dose 1 is defined as the mean of the assessments at day -7 and day 0; for dose 2 baseline is defined as the mean of the three assessments at day -7, day 0 and day 60 (day 0 for dose 2).

\*\*Note: The post-vaccination completion of SF-36 and EQ-5D questionnaires brought home by the subjects will be on days 1 to day 6, with day 7 to be filled in at the site (during Visits 3 and 5); while the post-vaccination recording of solicited AEs on the diary card brought home by the subjects will be on days 0 to day 6.

## 5. STUDY POPULATION

### 5.1. Total Vaccinated cohort

The Total Vaccinated Cohort (TVC) will include all vaccinated subjects with respect to the vaccine actually administered.

The TVC for analysis of safety will include all subjects with at least one vaccine dose administered.

The TVC for analysis of reactogenicity will include all subjects with at least one vaccine dose administered and documented.

# Statistical Analysis Plan

Study alias & e-track number(s): ZOSTER-063 (204928)

## 5.1.1. According-to-protocol cohort for analysis of safety

The ATP cohort for analysis of safety will include all subjects:

- who met all eligibility criteria (i.e. no protocol violation linked to the inclusion/exclusion criteria, including age);
- who have received at least one dose of study vaccine;
- for whom administration site of study vaccine is known;
- who have not received other vaccine forbidden in the protocol (Section 6.5.2 in the protocol);
- Who have received the study vaccine correctly reconstituted.
- Who received the vaccine according to protocol procedures (i.e. no temperature deviation and no expired vaccine).

The list of applicable elimination codes for each cohort can be found in the study specific form FORM-BIO-CLIN-9004-05 Criteria for eliminating subjects from the analyses.

Cohort	Elimination codes	Eli Type
ATP cohort for analysis for safety	1010-1600	MA

## 6. STATISTICAL METHODS

### 6.1. Analysis of demographics/baseline characteristics

Demographic characteristics (age, gender, geographic ancestry and ethnicity) will be tabulated.

The mean age (plus range and standard deviation) of the enrolled subjects, as a whole, and stratified by age group will be calculated.

The distribution of subjects enrolled among the study sites will be tabulated as a whole.

The demographics characteristics will also be tabulated by age stratum and frailty status (sub-groups are defined in [Table 1](#)).

# Statistical Analysis Plan

GlaxoSmithKline

Study alias & e-track number(s): ZOSTER-063 (204928)

## 6.2. Analysis of Quality of Life (QoL)

The primary endpoint analysis will be based on the Total Vaccinated Cohort (TVC).

### 6.2.1. SF-36 and EQ-5D

The SF-36 health survey and the EQ-5D questionnaires will be completed by all subjects at each study visits (i.e., Visit 1 Day -7, Visit 2 Month 0 (before the vaccination), Visit 3 Day 7, Visit 4 Month 2 (before the vaccination) and Visit 5 Day 67). Additionally, after each vaccination, the subjects will be given the questionnaires to take home and asked to complete only questions 3a through 3j of the SF-36 questionnaires and the entire EQ-5D questionnaires, on a daily basis on Days 1 to 6 post-vaccination.

Each of the 8 components of the SF-36 Questionnaire and the EQ-5D Utility and VAS scores will be presented at each scheduled visit (Day -7, Day 0, Day 7, Day 60 and Day 67) including the derived baseline values for each dose. In addition the SF-36 physical functioning score (PF) (based on questions 3a to 3j) and the EQ-5D utility and VAS scores will be presented on days 1 to 6 following each dose. Further details of the SF-36 components and EQ-5D Utility and VAS scores can be found in section [7.1.3](#).

The primary endpoint variable is the SF-36 Physical Functioning (PF) scale. The analysis will be performed on the subgroups detailed in [Table 1](#).

The 10 individual questions that form the SF-36 PF scale will be analysed on an individual basis. The three responses (Limited a lot, Limited a little, Not limited at all) to the individual questions will be assigned a score of 0, 50, or 100. In this way a baseline score and a mean score over the 7 days post each dose can be calculated for each individual question. Summary statistics of the change from baseline will be presented for each individual question.

